5.15. Additional Efficacy Analysis

The following additional efficacy endpoints will be evaluated:

5.15.1.1. Free Fraction of the FXa Inhibitor

The Free Fraction Plasma Concentration (ng/mL; also known as unbound plasma fraction) of apixaban, rivaroxaban, and edoxaban will be evaluated at Baseline (prior to andexanet treatment), and at EOB, EOI, 4, 8, and 12 hours after the end of andexanet infusion. In addition, % Protein Binding will be determined.

Change and percent change from baseline in Free Fraction of the inhibitor to the minimum value during and and an administration (i.e., minimum value between (EOB and EOI), and to each time point will be calculated. Mean, median, standard deviation, minimum, and maximum value, and 95% CI for the median will be presented. Confidence interval will be estimated using distribution free procedure as described above for primary efficacy analysis. In addition, the time course of unbound inhibitor concentrations following and an analysis will be presented. Protein Binding will be presented as listings.

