2.3. Exploratory Efficacy Objectives

- For patients receiving apixaban, rivaroxaban, or edoxaban, to evaluate the decrease in the free fraction of the FXa inhibitor following and examet treatment.
- To evaluate the effect of and exanet on thrombin generation.
- To evaluate the effect of and examet on levels of Tissue Factor Pathway Inhibitor (TFPI).
- To evaluate the effect of and examet on levels of Antithrombin III (ATIII).
- To evaluate the effect of and examet on levels of anti-factor IIa activity.
- To evaluate hemostatic efficacy in ICH patients at high risk for hematoma expansion.
- To evaluate the use of red blood cell transfusions.
- To evaluate the use of other blood products and hemostatic agents.
- To evaluate the occurrence of re-bleeding in patients following and examet treatment. Re-bleeding is defined as follows: bleeding from the same (or a different) anatomical site in patients within 24 hours of initial and examet treatment and after achieving initial good/excellent hemostasis.
- For patients with ICH, to evaluate change in clinical status following and exanet treatment.

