In the andexanet Phase 2 study where andexanet was administered to healthy human subjects who had been treated with apixaban 5 mg PO BID, multiple cohorts of both andexanet bolus alone (90 mg, 210 mg, and 420 mg) and bolus + infusion regimens (420 mg + 4 mg/min for 45 minutes or 120 minutes) were investigated. These data showed that a molar ratio of more than 1.3:1 andexanet to total apixaban plasma concentration was needed to reverse anticoagulation as measured by anti-fXa activity (by 91-95%). This reversal directly correlated with the decrease in unbound fraction of apixaban, which decreased from 6.1% prior to andexanet administration to less than 0.5% at the end of the bolus infusion (a 92% decrease), demonstrating sequestration of the anticoagulant. Moreover, when a continuous (45-minute or 120-minute) infusion was added, the reversal of anti-fXa activity was maintained for the duration of the continuous infusion.

In the andexanet Phase 2 study where andexanet was administered to healthy human subjects who had been treated with rivaroxaban 20 mg PO QD, multiple cohorts of both andexanet bolus alone (210 mg, 420 mg, and 600 mg) and bolus + infusion regimens (720 mg + 4 mg/min for 120 minutes and 800 mg + 8 mg/min for 120 minutes) were investigated. The results showed that a 1.1 to 1.3:1 molar ratio of andexanet to total rivaroxaban plasma concentration was needed to reverse anticoagulation as measured by anti-fXa activity (average 76–81% decrease at the end of the bolus). This reversal directly correlated with the decrease in unbound fraction of rivaroxaban, which decreased from 24.5 ng/mL prior to andexanet administration to 5.1 ng/mL at the end of the bolus infusion (a 79.7% decrease), demonstrating sequestration of the anticoagulant. Moreover, when a continuous (120-minute) infusion was added, the reversal of anti-fXa activity was maintained for the duration of the continuous infusion. The change in dose from 420 mg used in the Phase 2 study to 400 mg in this study (14-505) and in the Phase 3 study (14-504) is due to the change in formulation and concentration of andexanet between the frozen formulation (3 mg/mL) and the lyophilized formulation (10 mg/mL).

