11.6. Determination of Sample Size

The initial sample size is based on the second primary efficacy variable. A sample size of 162 efficacy evaluable patients will provide 80% power for a two-sided 95% CI that is completely above 50% for the second primary efficacy variable of effective hemostasis, demonstrating a response rate above 50% for that variable. This is based on an anticipated response rate of 61%. Further details on the sample size calculation are provided in the SAP.

The power to demonstrate a decrease in anti-fXa activity is expected to be higher than that to demonstrate a change in hemostatic efficacy. In prior studies in healthy normal subjects, the mean percent change in anti-fXa activity was -93.9 with a standard deviation of 1.7 within 5 minutes of the end of the administration of a bolus of andexanet, compared to -20.7 (8.6) within 5 minutes of the end of the administration of a bolus of placebo, among subjects who had received apixaban dosed to steady state. With 162 patients in the Efficacy Analysis Population with baseline anti-fXa activity of at least 75 ng/mL for patients receiving apixaban and rivaroxaban, 40 ng/mL for patients receiving edoxaban, and 0.25 IU/mL for patients receiving enoxaparin, the power to demonstrate that the true percent change is less than 0 is over 99%.

It is estimated that approximately 30% of the andexanet-treated patients will have pre-andexanet anti-fXa activity of < 75 ng/mL for patients receiving apixaban and rivaroxaban, < 40 ng/mL for patients receiving edoxaban, and 0.25 IU/mL for patients receiving enoxaparin, and therefore these patients will not be included in the primary analysis. Additionally, it is estimated that up to 5% of patients will be unevaluable for reasons unrelated to andexanet. In addition, enrollment will continue until at least 110 evaluable ICH patients (50 of whom are deemed to be high risk) are enrolled to more comprehensively capture clinical outcomes in this high risk patient population. Therefore, it is anticipated that up to 250 patients may have to be treated to achieve the requisite number of evaluable patients.

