2.3. Exploratory Efficacy Objectives

- For patients receiving apixaban, rivaroxaban, or edoxaban, to evaluate the decrease in the free fraction of the FXa inhibitor following andexanet treatment.
- To evaluate the effect of andexanet on thrombin generation.
- To evaluate the effect of andexanet on levels of tissue factor pathway inhibitor (TFPI).
- To evaluate the effect of and examet on levels of antithrombin III (ATIII).
- To evaluate the effect of andexanet on anti-factor IIa levels for patients receiving enoxaparin.
- To evaluate hemostatic efficacy in intracranial hemorrhage (ICH) patients at high risk for hematoma expansion.
- To evaluate the use of red blood cell transfusions.
- To evaluate the use of other blood products and hemostatic agents.
- To evaluate the occurrence of adjudicated re-bleeding in patients following andexanet treatment. Re-bleeding is defined as follows: recurrent bleeding from the same or another anatomical site, or new bleeding from a different anatomical site in patients within 24 hours of initial andexanet treatment and after achieving initial good/excellent hemostasis. For patients with ICH, to evaluate change in clinical status following andexanet treatment.

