4.5. Other Efficacy Endpoints

4.5.1. Free Fraction of the FXa Inhibitor

The free fraction plasma concentration (ng/mL; also called the unbound plasma fraction) of apixaban, rivaroxaban, and edoxaban will be evaluated at Baseline (prior to andexanet treatment), and at EOB, EOI, 4, 8, and 12 hours after the EOI. In addition, % Protein Binding and Total Plasma Concentration (ng/mL) will be determined.

Change and percent change from baseline in free fraction of the inhibitor to the minimum value during and exanet treatment administration (i.e., minimum value between (EOB and EOI), and to each time point will be calculated. Values reported as <0.03125 will be replaced with 0.03125.

4.5.2. Tissue factor pathway inhibitor (TFPI)

TFPI parameters were collected, starting with Protocol Amendment 4 at baseline, EOI, 4, 8, 12, 24, 48, and 72 hours, and 7 days post and exanet treatment. TFPI Activity, Free TFPI antigen, and Total TFPI antigen will be determined.

Values < 0.2 will be replaced with $\frac{1}{2}$ of LLOQ (i.e., 0.1). TFPI parameters will also be summarized as part of the safety analysis.

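### The exploratory free-fraction objective is summarised only as unbound concentration, which in a single-arm trial mixes andexanet's effect with drug elimination; the data for the fraction itself get no summary

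*SAP*

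**What the plan says.** The exploratory objective for apixaban, rivaroxaban and edoxaban is "to evaluate the decrease in the free fraction of the FXa inhibitor following andexanet treatment" (SAP 2.3; Protocol 2.3 has the same objective).

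SAP 5.15.1.1 names the variable as "The Free Fraction Plasma Concentration (ng/mL; also known as unbound plasma fraction) of apixaban, rivaroxaban, and edoxaban", and SAP 4.5.1 defines it in the same units. The analysis is "Change and percent change from baseline in Free Fraction of the inhibitor to the minimum value" of end of bolus (EOB) and end of infusion (EOI), and also to each time point through 12 h after EOI, with a distribution-free 95% CI for the median. The sample Tables 14.2.4.1a-c and the matching figures are titled as unbound concentration.

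On the quantities that would give a ratio, SAP 4.5.1 says: "In addition, % Protein Binding and Total Plasma Concentration (ng/mL) will be determined". SAP 5.15.1.1 then says "Protein Binding will be presented as listings" (Listing 16.2.6.9). No table, figure or listing is named for total concentration, and no summary of unbound/total is planned.

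The study has one arm and no control (SAP 3.3).

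**The concern.** Unbound concentration falls as the inhibitor is eliminated, whether or not andexanet is given. With no control arm, nothing in the planned analysis separates that fall from the fall caused by andexanet binding the drug, and the SAP gives no method for doing so. The ratio of unbound to total drug is less exposed: if elimination lowers both in the same proportion, the ratio stays put and a fall in it points to sequestration.

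At stake is how the exploratory result can be read, above all the changes from baseline at 4, 8 and 12 h after infusion. At those times a large fall in concentration could be reported under a free-fraction heading although much or most of it may be elimination.

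**Working it through.** **1. The protocol's own figures.** Protocol 3.4.4 gives the apixaban unbound fraction in percent, "which decreased from 6.1% prior to andexanet administration to less than 0.5% at the end of the bolus infusion", stated as a 92% decrease. Check: 100 x (1 - 0.5/6.1) = 91.8%, which agrees. The next paragraph gives the rivaroxaban unbound fraction as 24.5 to 5.1 ng/mL, stated as 79.7%. Check: 100 x (1 - 5.1/24.5) = 79.2%, close but not exact (it could be a mean of individual changes). So one section uses one term on two scales, and the expected early fall is about 80-92%.

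**2. Half-life.** Protocol 3.4.2 puts the rivaroxaban level at 18 h at about twice the mean 24 h trough. Halving over 24 - 18 = 6 h implies a half-life h of about 6 h. The documents give no such figure for the other inhibitors, so 4-12 h is used as an assumed range.

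**3. Fall from elimination alone.** Formula: 100 x (1 - 2^(-t/h)), with t in hours from the start of the bolus. The bolus takes 15-30 min and the infusion about 120 min, so EOB is at 0.25-0.5 h and EOI at 2.25-2.5 h. Later times use a 30-min bolus. Example: h = 6, t = 2.5 gives 100 x (1 - 2^(-0.417)) = 25.1%.

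| h | EOB | EOI | EOI+4 h (t = 6.5) | EOI+8 h (t = 10.5) | EOI+12 h (t = 14.5) |
|---|---|---|---|---|---|
| 4 h | 4.2-8.3% | 32.3-35.2% | 67.6% | 83.8% | 91.9% |
| 6 h | 2.8-5.6% | 22.9-25.1% | 52.8% | 70.3% | 81.3% |
| 8 h | 2.1-4.2% | 17.7-19.5% | 43.1% | 59.7% | 71.5% |
| 12 h | 1.4-2.8% | 12.2-13.4% | 31.3% | 45.5% | 56.7% |

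Protocol Appendix A allows the EOB sample up to 30 min after the bolus ends. After a 30-min bolus that is t = 1 h, and at h = 6 the fall is 100 x (1 - 2^(-1/6)) = 10.9%.

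**4. The same on the fraction.** If elimination multiplies unbound U and total T by the same factor k, then kU/kT = U/T and the expected change is 0 at any single time point. This assumes that binding does not depend on concentration.

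**5. What the planned interval would show with no andexanet effect.** Simulation, 4,000 runs per setting, h = 6 h, assumed n = 20, 50 or 100 per inhibitor and assumed measurement CV of 10% or 20%. At EOI the distribution-free CI for the median change in concentration lay wholly below 0 in 93-100% of runs. For the fraction at EOI it did so in about 1.4-2.1%.

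**6. The on-treatment minimum.** Taking the smaller of two noisy values biases the result downward on either scale. With no effect, the minimum of the fraction at EOB and EOI showed a median change of about -5% (CV 10%) to -10% (CV 20%). Its CI lay below 0 in about 29% of runs at n = 20, 59% at n = 50 and 90% at n = 100.

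**7. Controlled data in the protocol.** In the placebo-controlled Phase 3 studies (Protocol 1.4.4, legend to Figure 8), unbound concentration differed significantly from placebo only until 1 h (apixaban) or 3 h (rivaroxaban) after the infusion ended. Lack of significance later does not prove lack of effect. It does show that falls from baseline at 4 h and beyond need a comparator or a measure that elimination does not move.

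**The case against.** Three stronger readings are tempting, and the documents do not support them.

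- *The SAP quietly swapped the variable.* It did not. Protocol 3.4.4 gives rivaroxaban's unbound fraction in ng/mL, Protocol 10.1.2-10.1.4 speaks of unbound plasma levels, and the SAP states its units. Protocol 3.4.3 also gives a reason to analyse concentration: unbound apixaban, not total, tracks anti-fXa activity. Concentration is a defensible measure and should stay.
- *The placebo result proves the size of the elimination effect.* Protocol 11.6 reports the andexanet change "compared to -20.7 (8.6) within 5 minutes of the end of the administration of a bolus of placebo". That is anti-fXa activity, not unbound drug, in healthy subjects just after a bolus. Elimination over 15-30 min is only about 1-6% for half-lives of 6-12 h, so most of that figure is something else. It says nothing about a fall over 2.25-2.5 h and is not used here.
- *The early fall could be an artefact.* At EOB, elimination accounts for a few percent, or about 11% at the latest permitted draw with h = 6 h, against an expected 80-92%. The qualitative conclusion there would hold.

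Two further limits stand. No document says that protein binding is constant, and bleeding patients receive colloid, crystalloid and blood products, so a zero expected change in the fraction is an assumption. Patients still absorbing drug (Protocol 1.4.3 places the peak about 3 h after dosing) may show no elimination fall at first. It is also fair that the objective is exploratory, has no success rule, and that SAP 5.1 allows extra tables in the study report.

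**Conclusion.** The point holds as a minor one. The free-fraction objective is ambiguously labelled and summarised only as a concentration, although the data for the fraction are collected. Elimination alone contributes a few percent to the measured fall at EOB, about 12-25% at EOI for half-lives of 6-12 h, and about 53-81% at EOI+4 to EOI+12 h for a half-life of 6 h. The later range is 31-57% at 12 h and 68-92% at 4 h. The planned changes at those later times therefore cannot be attributed to andexanet.

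This rests on first-order elimination, on the 6 h half-life inferred for rivaroxaban and assumed values elsewhere, and, for the advantage of the fraction, on concentration-independent binding. Neither primary endpoint is affected.

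**What to change.** In SAP 4.5.1 and 5.15.1.1:

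- Derive free fraction (%) = 100 x unbound/total, or 100 minus % protein binding, at each time point.
- Summarise its value and change from baseline by direct inhibitor at EOB, EOI and EOI+4, +8 and +12 h separately, with the distribution-free 95% CI for the median. Do not rely on the minimum of EOB and EOI.
- Keep unbound concentration (ng/mL) as a second measure with its own name, and use the two names consistently.
- State that attributing a fall in the fraction to andexanet assumes concentration-independent protein binding.
- Say how the fraction is formed when the unbound value has been set to the 0.03125 floor in SAP 4.5.1.

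Cost: one more summary table per direct inhibitor, from data already collected, with no change to study conduct.

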5.15.1.2. Thrombin Generation

Thrombin generation will be measured from plasma samples at Baseline, EOB, EOI, 4, 8, 12, 18, 24, 48, 72 hours post and examet treatment, and Day 30. Five parameters related to thrombin generation will be measured: Endogenous Thrombin Potential (ETP), peak height, time to peak height, lag time, and velocity index.

ETP (nM*min) is prospectively identified as the primary measure for thrombin generation. The time course for ETP will be plotted for each FXa inhibitor. In addition, change and percent

change from baseline to peak ETP will be calculated, and change from baseline for each time point will be calculated. Peak is the largest value between end of andexanet bolus and ending of infusion for each subject. Mean, median, standard deviation, minimum, and maximum value, and 95% CI for the median will be presented. Confidence interval will be estimated using distribution free procedure as described above for primary efficacy analysis. Similar analysis will also be performed for Non-TF Endogenous Thrombin Potential.

The other Thrombin generation parameters (i.e., peak height, time to peak height, lag time, and velocity index, non TF ETP peak height, time to peak height, lag time, and velocity index) will be presented in a summary table for each time point and in a data listing by patient.

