11.5.4. Exploratory Efficacy Endpoints

The following additional efficacy endpoints will be analyzed as exploratory:

- The number of patients receiving one or more red blood cell transfusions from the start of the andexanet bolus through 12 hours after the end of andexanet infusion.
- For patients receiving apixaban, rivaroxaban, or edoxaban, to evaluate the decrease in free fraction of the FXa inhibitor following and examet administration.
- The number of red blood cell units transfused per patient from the start of the andexanet bolus through 12 hours after the end of the andexanet infusion.
- The use of non-study-prescribed blood products and/or hemostatic agents.
- The occurrence of re-bleeding following and examet treatment. Re-bleeding is defined as follows: recurrent bleeding from the same or another anatomical site, or new bleeding from a different anatomical site within 24 hours of initial and examet treatment and after achieving initial good/excellent hemostasis.
- Andexanet reversal of anticoagulant effect as measured through TG parameters (with, Endogenous Thrombin Potential [ETP] as the primary measure), for both the Tissue Factor (TF)-initiated assay and the non-TF-initiated assay.
- TFPI levels, both free and total, pre- and post-administration of andexanet.
- ATIII levels, pre- and post-administration of andexanet.
- Anti-factor IIa levels, pre- and post-administration of andexanet (enoxaparin patients only).
- The achievement of hemostatic efficacy in ICH patients at high risk of hematoma expansion.
- Change from baseline in GCS at 1 hour, 12 hours, and 30 days (for ICH patients only).
- Change from baseline in mRS at 1 hour, 12 hours, and 30 days (for ICH patients only).
- Change from baseline in NIHSS at 1 hour, 12 hours, and 30 days (for ICH patients only).

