Samples for anti-fXa activity and unbound anticoagulant should be drawn at two time points; one at (or within 30 minutes after) the end of the bolus, and another at (or within 30 minutes prior to) the end of the infusion.

¹² Window: Days 30–37. Patients who discontinue from the study after receiving any amount of andexanet but before this visit should undergo all follow-up safety procedures, unless the patient also explicitly withdraws consent for these procedures, in which case they should undergo an Early Termination visit.

¹³ Record dates of use of anticoagulant(s) on the anticoagulant CRF.

¹⁴ Laboratory sampling procedures required for re-dosed patients pertain to anti-fXa activity only.

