5.0 STATISTICAL METHODS

5.1. General Considerations

All hypothesis tests will be 2-sided and reported at the 0.05 significance level. All CIs will be 2-sided and reported at the 95% confidence level unless stated otherwise. P-values will be rounded to 3 decimal places. P-values less than 0.001 will be presented at p < 0.001.

For continuous variables, the number of non-missing observations, mean, median, quartiles, standard deviation, minimum, maximum, and 95% confidence interval (CI) will be presented unless stated otherwise. Means, medians, quartiles, and 95% CI will be displayed to 1 more decimal place than the raw data and the standard deviation will be displayed to 2 more decimal places. The minimum and maximum will be displayed to the same number of decimal places as reported in the raw data. For categorical variables, the number of observations, the number of events, and percentages of events with the 95% CI will be reported. Descriptive summaries will be presented for the efficacy population as well as for the individual subgroup analyses.

It is anticipated that all statistical analyses will be performed using SAS Version 9.4 (SAS Institute, Inc., Cary NC) or higher. Additional software may be used for the production of graphics and for statistical methodology not provided by SAS. All summaries and analyses documented in this Statistical Analysis Plan (SAP) will be presented in the final integrated CSR. The CSR may also contain additional tables or statistical tests as warranted by the data obtained. The justification for any such additional analyses will be fully documented in the CSR.

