5.13.1. Primary Efficacy Analysis

Two primary endpoints will be evaluated:

- The percent change from baseline in anti-fXa activity to the on treatment nadir (i.e., minimum value between EOB and EOI).
- The achievement of hemostatic efficacy of stopping an ongoing major bleed at 12 hours from the end of the andexanet infusion, rated by the independent EAC as excellent or good.

The first objective is to demonstrate the decrease in anti-fXa activity following and examet treatment. Analysis will include all patients in the efficacy population. The following hypothesis will be evaluated:

Ho:
$$\mu = 0$$

H₁:
$$\mu \neq 0$$

The percent change in anti-fXa activity from baseline (last measurement before administration of andexanet) to post administration (the lowest level measured between the start of andexanet administration and 10 minutes after the end of the andexanet administration) will be calculated for each patient as %change = $100 \times (post - baseline)$ / baseline rounded to 1 decimal place. Percent change from baseline in anti-fXa activity will be evaluated using a distribution free two-

sided 95% CIs for the median. Because the data are expected to be non-normal, the distribution free confidence interval will be the primary for decision making. If the CI for the median excludes 0, the first primary objective will be considered to have been met. The CI will be calculated using distribution free methods using PROC UNIVARIATE in SAS as shown below.

```
proc univariate ciquantdf (alpha=.05);
var val;
ods output Quantiles=results;
run;
```

The second primary objective is to evaluate the hemostatic efficacy following and exanet treatment. Analysis will be performed including all patients in the efficacy population with valid EAC hemostatic efficacy adjudication (excluding events adjudicated as non-evaluable due to administrative reason). In addition, a sensitivity analysis will be conducted with the patients adjudicated as non-evaluable due to administrative reason rated as poor hemostatic efficacy.

The following hypothesis will be evaluated:

```
H_0: \pi = 0.50
```

 H_1 : $\pi \neq 0.50$

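### The ETP change-to-peak summary sets the larger of two post-dose values against one baseline, so its CI can lie above zero far more often than 2.5% when ETP has not changed

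*SAP*

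**What the plan says.** Protocol 11.5.4 lists, among the exploratory efficacy endpoints, "Andexanet reversal of anticoagulant effect as measured through TG parameters", with ETP as the main measure, for both the TF-initiated and the non-TF-initiated assay.

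SAP 5.15.1.2 plans two kinds of ETP contrast. It states that change and percent "change from baseline to peak ETP will be calculated, and change from baseline for each time point will be calculated". Percent change is therefore attached to the peak contrast; the time-point contrast is absolute change. The peak is defined as follows: "Peak is the largest value between end of andexanet bolus and ending of infusion for each subject". SAP 4.5.3 repeats this definition.

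The statistics are stated next: "Mean, median, standard deviation, minimum, and maximum value, and 95% CI for the median will be presented". The method is the one used for the first primary endpoint: "Confidence interval will be estimated using distribution free procedure as described above for primary efficacy analysis". The same is to be done for non-TF ETP, and the ETP time course is plotted by FXa inhibitor.

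Two thrombin-generation samples fall between end of bolus and end of infusion in the Appendix A schedule. The footnote marked on those two cells sets the timing: "one at (or within 30 minutes after) the end of the bolus, and another at (or within 30 minutes prior to) the end of the" (cut here; the second sample is tied to when the infusion stops). Its wording names anti-fXa activity and unbound anticoagulant, but the mark stands on the thrombin-generation row. SAP 4.5.3 says that EOB and EOI thrombin-generation samples exist only from Amendment 4. SAP 5.13 runs efficacy analyses separately by FXa inhibitor, with pooling only where indicated. SAP 3.3 confirms a single arm.

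**The concern.** The peak contrast takes the maximum after dosing and a single value before it. If ETP does not move and the readings merely vary within a patient, the larger of two will exceed the one baseline more often than not. The median change is then positive with no drug effect, always in andexanet's favour. Neither SAP section corrects for taking the maximum, and no control arm is available to cancel it.

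What is at stake is how the ETP table is read. ETP is the named main measure of thrombin generation. Protocol 3.4.3 says the non-TF assay was added to find the TFPI-independent effect of andexanet, so the size of that effect is an open question. The only percent-change figure planned for either assay is the biased one. A reader who sees a median percent rise with an interval above zero may take it as restored thrombin generation when some or all of it is selection of the higher reading.

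**Working it through.** **Figures in the plan.** The documents state no sample size, variability, power or error rate for ETP, so there is no ETP figure to reproduce. The one stated sample size (162 patients, 80% power, 61% against 50%) concerns hemostasis. It reproduces by exact binomial (at least 94 responders, one-sided alpha 0.0246, power 80.5%) but does not bear on ETP.

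**Inputs from the documents.** One baseline (B), two post-dose values (EOB, EOI), peak = max(EOB, EOI). The CI comes from the SAP 5.13.1 code, "proc univariate ciquantdf (alpha=.05", and is two-sided under SAP 5.1: "All CIs will be 2-sided and reported at the 95% confidence level unless stated otherwise".

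**Assumptions.** No change in ETP; equal within-patient variance at the three times; no ties; every patient has all three samples. The correlation r is that between EOB and EOI deviations beyond whatever both share with baseline. Correlation shared equally by all three does not reduce the bias.

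**Step 1: chance that a patient's change-to-peak is negative.** Both EOB − B and EOI − B must be negative. Their correlation is c = (1 + r)/2, and for normal deviations

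q = 1/4 + arcsin(c)/(2π).

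- r = 0: c = 0.50, q = 0.333. Baseline is the largest of three exchangeable values one time in three; this case needs no normality.
- r = 0.5: c = 0.75, q = 0.385.
- r = 0.8: c = 0.90, q = 0.428.
- One fixed time point: q = 0.5.

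**Step 2: when the CI lies above zero.** The distribution-free interval runs from the k-th smallest to the k-th largest change. Here k is the largest rank with P(Bin(n, 0.5) ≤ k − 1) ≤ 0.025, which gives k = 10, 18 and 40 at n = 30, 50 and 100. The interval is wholly above zero when at most k − 1 changes are negative, so the probability is P(Bin(n, q) ≤ k − 1).

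| Contrast, no change in ETP | n = 30 | n = 50 | n = 100 |
|---|---|---|---|
| Peak, r = 0 | 43% | 60% | 90% |
| Peak, r = 0.5 | 22% | 31% | 58% |
| Peak, r = 0.8 | 11% | 13% | 25% |
| One fixed time point | 2.1% | 1.6% | 1.8% |

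The rate does not depend on the size of the noise. A log-normal simulation at n = 100 with r = 0 gave 89% to 91% for within-patient SDs from 0.05 to 0.30.

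**Step 3: size of the spurious rise.** The mean of the larger of two normal deviations is SD × √((1 − r)/π), that is 0.56, 0.40 and 0.25 within-patient SD at r = 0, 0.5 and 0.8. The median change is close to this. The documents give no SD. At an assumed SD of 0.10 on the log scale (CV about 10%) the rise is about 6%, 4% and 3%. At 0.20 it is about 12%, 8% and 5%.

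**The case against.** The strongest reply is that the effect on the report may be small, and several parts of it stand.

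- **It need not happen usually.** A reader might infer that the CI will usually exclude zero by chance. The documents do not support that. Analyses are by inhibitor, the samples start with Amendment 4, and Protocol 3.1 aims to hold indirect inhibitors to 20% or less of enrolment, so some sets may be small. EOB and EOI are both on-drug samples around one infusion of about two hours, while the baseline sample may be drawn up to three hours before dosing. Excess EOB-EOI correlation is therefore plausible. A majority rate needs about 42 or more patients with near-exchangeable values; at r = 0.8 the rate is 25% even at n = 100. Patients with only one of the two post-dose samples dilute the bias further.
- **No ETP test is planned.** A reader might infer one from the shared CI method. The rule about excluding zero in SAP 5.13.1 belongs to the anti-fXa primary endpoint; SAP 5.15.1.2 borrows only the interval calculation. No primary or secondary conclusion depends on ETP.
- **An unselected contrast is already there.** Change at each time point and the time-course plot are planned in the same section, and nothing names the peak as the sole or headline measure.

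What the reply does not remove: the peak contrast is still reported with an interval that ignores the selection, and percent change is planned for that contrast alone. A large true effect could make the bias unimportant, but the documents give no expected ETP effect in bleeding patients against which to judge it.

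**Conclusion.** The point holds in a limited form. With ETP unchanged, the change-to-peak summary is biased in andexanet's favour. Its CI lies wholly above zero in 11% to 90% of trials over the 30 to 100 patients and correlations of 0 to 0.8 examined, against about 2% for one fixed time point. Where the trial falls in that range cannot be settled, because neither the number of patients with all three samples nor the ETP variability is given. The percent rises rest on assumed CVs.

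This is a cheap improvement to an exploratory summary. It does not undermine the trial's efficacy conclusions, and the plan does not leave ETP without an unselected contrast.

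**What to change.** In SAP 4.5.3 and 5.15.1.2, for both ETP and non-TF ETP:

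- report change and percent change from baseline with the distribution-free 95% CI for the median at two fixed time points, EOI as the lead and EOB second;
- keep change-to-peak as a descriptive value without a CI, labelled as biased upward because it selects the larger of two readings;
- state the number of patients contributing to each row.

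The cost is SAP wording and a table change. No new data are needed, since change at each time point is already derived. The stated effect will be slightly smaller, and patients without an EOI sample drop from that row.

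The change removes the selection bias and nothing more. A reader might infer that a fixed-time rise would then show andexanet's effect. Without a control arm, ETP may also rise as the anticoagulant clears naturally during dosing, and the report should say so.
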